## 9 PHARMACOKINETICS

### 9.1 Plasma concentrations of PSL and its major metabolites

Concentrations of PSL and its major metabolites will be determined from blood samples obtained during the Titration and Stabilization and Maintenance Periods (Visits 3, 4, 5, 6 and 7). Individual concentrations of PSL, [REDACTED] (from venous conventional sampling and dried blood (MITRA) sampling) and [REDACTED] (from venous conventional sampling) will be listed for subjects in PSL treatment groups for the PK-Set and will include visit, actual daily dose (mg), date and time of the most recent administration, scheduled sampling time per the CRF, actual date and time of sampling, time interval between plasma sample and the most recent administration (in hours with 2 decimal places). Samples excluded from the PK-PPS will be marked in the listing.

Values below the limit of quantification (LOQ) will be reported as BLQ (below the limit of quantification).

Concentrations of PSL and its [REDACTED] metabolite will be summarized by sampling method (venous, dried blood MITRA), PSL dose group, visit, and sampling times for the PK-PPS using the following descriptive statistics: number of observations, geometric mean, 95% CI of the geometric mean, geometric coefficient of variation, arithmetic mean, SD, median, and minimum and maximum values. Measured values below the LOQ will be excluded for the calculation of descriptive statistics but listed. Concentrations for [REDACTED] (only in venous blood) will also be summarized similarly. Only PSL samples taken up to the (date of the last dose of study medication +1) will be included in the summary.

Of note, geometric mean is calculated as:  $\exp(\text{arithmetic mean of log-transformed concentrations})$ ; upper and lower bounds of the 95% confidence interval (CI) of the geometric mean are calculated as  $\exp(\text{upper})$  and  $\exp(\text{lower})$  of the 95% CI of the arithmetic mean of log-transformed concentrations; geometric coefficient of variation is calculated as:  $100 \times \sqrt{[\text{variance of log-transformed concentrations}] - 1}$ .

The PK samples will be summarized based on the actual time since the most recent dose using the following time categories:

- >0 to <45 min after dosage: 0.5h (30min)
- 45 to <75 min after dosage: 1h (60min)
- 75 to <105 min after dosage: 1.5h (90min)
- 105 to <150 min after dosage: 2h (120min)
- 150 to <210 min after dosage: 3h (180min)
- 4h: 3.5h to <4.5h
- 5h: 4.5 to <5.5h
- 6h: 5.5 to <6.5h
- 8h: 6.5 to <9h
- 10h: 9h to <11h or >-3h to <-1h

- 12h: 11h to <14h or >=-1h to <=0 (time points for the trough concentration,)

The geometric mean and associated 95% CI for the trough concentrations of PSL and [REDACTED] from MITRA will be presented by PSL treatment group and visit using semi-log plots.

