5.4.2 Rationale for dose selection

Dose selection for EP0091 was informed by data derived from the following:

1. UP0036: PET-derived human SV2A receptor occupancy vs exposure relationship
2. N01383: PET-derived human GABA-A receptor occupancy
3. The maximum tolerated dose (MTD) of 400mg bid in Phase 1
4. EP0069: efficacy-exposure analysis
5. Preclinical pharmacological exposure-response data

Four dose levels of PSL (equally spaced on the logarithmic scale), 100mg/day, 200mg/day, 400mg/day, and 800mg/day, administered bid have been selected to fully explore the dose-response curve for PSL in patients with drug-resistant epilepsy.

Two PET studies, UP0036: PET-derived human SV2A receptor occupancy and N01383: PET-derived human GABA-A receptor occupancy, were performed to inform dose selection for the clinical studies. Using population-PK modeling of the PK and PET data with a SV2A ligand in UP0036, simulations projected SV2A receptor occupancy in human brain regions to be greater than 90% over the whole dosing interval for 90% of a population treated with the 400 and 300mg bid dosing, and greater than 90% for 75% of a population at 100mg bid dosing. In N01383, modeling of the receptor occupancy of PSL at brain GABA-A receptors measured using the PET ligand, flumazenil, demonstrated that subjects treated with PSL 200mg bid had maximal GABA-A receptor occupancy ranging from lower limit quantification (5%) to 9.7%. Subjects treated with PSL 400mg bid had maximal GABA-A receptor occupancy ranging from 7.6% to 16.8%.

The rationale for the selection of the maximum dose, 400mg bid (800mg/day), is based on the MTD seen in Phase 1 single dose and multiple dose clinical studies, and is in line with receptor occupancy at the SV2A receptor and the nonclinical data described above. Furthermore, 800mg/day has demonstrated clinically meaningful efficacy (EP0069 primary outcome analysis) with acceptable tolerability. The maximum dose is supported further by nonclinical data that demonstrate that high levels of SV2A receptor occupancy are required for efficacy in the primary model of resistant epilepsy (amygdala kindling, mean effective dose [ED₅₀]=95%). Conversely, receptor occupancy at the GABA site associated with efficacy was relatively low (ED₅₀=9%). Therefore, it is reasonable to conclude that the high dose level should be associated with occupancy consistent with these levels observed at SV2A and GABA-A receptors and maintained for SV2A.

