#### **3.5.7.2 Pharmacokinetic Per-Protocol Set (PK-PPS)**

A PK Per Protocol Set (PK-PPS) will be a subset of the PKS and identified for active treatment groups, which would exclude subjects or PK sample data points with major deviations that could impact PK evaluations e.g. when there is evidence that the sample collected is not at steady-state due to missing doses, dose alterations or interacting concomitant medications, etc. Subjects or PK sample data points to be excluded from this PK-PPS, will be identified during a pre-analysis data review.

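### SAP 9.1 drops PSL and metabolite concentrations below LOQ from its descriptive statistics and tabulates no count of them, so any such values would bias the summaries upward, most at trough and at 50mg bid

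*SAP*

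**What the plan says.** SAP 9.1 summarises PSL and metabolite concentrations on the PK-PPS by sampling method, dose group, visit and time category. The statistics are "number of observations, geometric mean, 95% CI of the geometric mean, geometric coefficient of variation, arithmetic mean, SD, median, and minimum and maximum values". The rule for low values is: "Measured values below the LOQ will be excluded for the calculation of descriptive statistics but listed". In the listings such values appear as BLQ.

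The 12h category, 11h to under 14h after dosing or the last hour before a dose, is labelled "time points for the trough concentration". For the MITRA samples, "The geometric mean and associated 95% CI for the trough concentrations of PSL" and its metabolite "will be presented by PSL treatment group and visit using semi-log plots".

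The current text asks for no BLQ count or percentage in the tables and sets no quantifiable share below which a statistic is withheld. Neither document states an LOQ, an expected BLQ rate, a concentration level or a between-subject CV. SAP 9.3 sends population and exploratory PK analyses to a separate PK Data Analysis Plan.

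**The concern.** A BLQ result is not missing: it says that the concentration is somewhere below a known limit. Removing these results cuts off the bottom of the distribution, so every summary then describes only the quantifiable samples. The geometric mean, arithmetic mean, median and minimum can only rise, and under a lognormal distribution the CV falls.

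The cut does not fall evenly. Protocol 5.4.2 sets out the arms: "Four dose levels of PSL (equally spaced on the logarithmic scale), 100mg/day, 200mg/day, 400mg/day, and 800mg/day, administered bid". That is an 8-fold range. With one assay limit and exposure that rises with dose, BLQ values would gather at trough and in the 50mg bid arm, where the fallback in Protocol Table 7-2 lowers the dose further to 50mg/day. The largest upward shift therefore falls on the lowest arm, and the plotted line across doses flattens.

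The table would not show that this had happened. The number of observations is itself one of the statistics from which BLQ values are excluded. A cell that was mostly BLQ would print a geometric mean and CI from its few highest values, with nothing beside it to warn the reader. In a dose-finding study these are descriptive displays of exposure by arm, so they should be right at whatever BLQ rate turns up.

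**Working it through.** There is no stated figure to reproduce, so the size is shown as a range.

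**Inputs from the documents.** The exclusion rule, statistics and trough plot (SAP 9.1), and doses of 50, 100, 200 and 400mg bid (Protocol 5.4.2).

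**Assumptions.** Lognormal concentrations; dose-proportional exposure, so the true 400/50mg bid ratio is 8.0 and the true log-log slope is 1.00; one LOQ and one CV at all doses; geometric CV of 40% to 150%; BLQ share p at 50mg bid of 1%, 10% or 30%; every BLQ value a real concentration from the same distribution.

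**Formulas.** Let s = √ln(1 + CV²), z = Φ⁻¹(p) and λ = φ(z)/(1 − p).
- Reported geometric mean ÷ true geometric mean = exp(s·λ).
- Log variance left after exclusion = s²(1 + zλ − λ²), and reported CV = √(exp(that variance) − 1). This is the usual definition of the geometric CV.
- At dose d, replace z by z − ln(d/50)/s.

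**One case in full: CV 100%, p = 10%.**
- s = √ln 2 = 0.833; z = −1.282; φ(z) = 0.1755; λ = 0.1755/0.9 = 0.195.
- Geometric mean at 50mg bid: exp(0.833 × 0.195) = 1.176, or 17.6% too high.
- Remaining log variance: 0.693 × (1 − 0.250 − 0.038) = 0.494, so the CV is shown as √(exp(0.494) − 1) = 80% instead of 100%.
- At 400mg bid the shifted z is −1.282 − 2.079/0.833 = −3.78. λ is then about 0.0003 and the bias is nil.
- Reported 400/50 ratio: 8/1.176 = 6.8.
- The median of the remaining 90% sits at the true 55th percentile: exp(0.833 × 0.126) = 1.11, or 11% too high.

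**Range** (first figure CV 40%, second CV 150%):

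| BLQ at 50mg bid | Bias in geometric mean, 50mg bid | Bias, 400mg bid | 400/50 ratio (true 8.0) | Slope (true 1.00) | CV shown at 50mg bid |
|---|---|---|---|---|---|
| 0% | 0% | 0% | 8.0 | 1.00 | 40%, 150% |
| 1% | +1.0% to +3.0% | 0.0% | 7.9 to 7.8 | 0.996 to 0.987 | 39%, 142% |
| 10% | +7.8% to +23.6% | 0.0% to +0.3% | 7.4 to 6.5 | 0.967 to 0.902 | 33%, 115% |
| 30% | +21.1% to +71.5% | 0.0% to +2.2% | 6.6 to 4.8 | 0.916 to 0.753 | 28%, 89% |

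**Alternatives under the same assumptions.** Maximum likelihood that treats BLQ values as left-censored has no bias in large samples. Substituting LOQ/2 gives −5.0% to −1.8% at 10% BLQ and −12.6% to −0.1% at 30% BLQ. That is better than exclusion in these cases, but it carries its own bias.

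**The case against.** The best defence is that nothing shows BLQ troughs will occur in numbers. With none the rule does no harm, and at 1% the bias is about 1% to 3%. The values are not hidden either: they are listed as BLQ, so a per-cell count can be rebuilt by hand. Both points stand. They limit the size and the certainty of the concern, but they do not justify a pre-specified rule that errs in a known direction whenever BLQ values arise.

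Four stronger readings are tempting, and the documents do not support them.

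- **That the low-dose means will be inflated.** This needs an LOQ or a BLQ rate, and neither is given.
- **That remaining BLQ values must be genuine low concentrations, because the PK-PPS removes missed doses.** SAP 3.5.7.2 allows exclusion "when there is evidence that the sample collected is not at steady-state due to missing doses, dose alterations or interacting concomitant medications". Missed doses without such evidence stay in. Compliance rests on tablet counts and recorded intake (SAP 7.1), and samples may be taken at home (Protocol 10.1.1.1). A BLQ trough could be either a true low value or undetected non-adherence. If it is the latter, a censored estimate would understate on-treatment exposure, which is one more reason to show the count.
- **That the venous and MITRA summaries would be distorted against each other.** This requires different LOQs for the two methods, which the documents do not state.
- **That the study's exposure-response or dose-selection conclusions are compromised.** SAP 9.1 plans no dose-proportionality test and no exposure model. Protocol 13.4.2 derives PK parameters from population modelling, and SAP 9.3 places that work in a separate plan whose BLQ handling is not visible here.

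SAP 14.2 records a different BLQ rule. That is superseded text, and no contradiction is claimed from it.

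**Conclusion.** The concern holds in conditional form. If BLQ samples occur, the SAP 9.1 tables and trough plots overstate the geometric mean, median and minimum and understate the CV, most at trough and at 50mg bid. The plot across doses could then look flatter than the true relation. At 50mg bid the geometric mean would be about 1% to 3% too high with 1% BLQ, 8% to 24% with 10%, and 21% to 72% with 30%; with no BLQ there is no bias.

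The direction follows from dropping the lowest values. Its concentration in the lowest arm needs only a common LOQ and exposure that rises with dose. The sizes rest on the lognormal form, the assumed CV range and the assumed BLQ shares. The ratios and slopes also rest on dose proportionality. None of these comes from the documents. Efficacy tests, sample size and the separately planned population PK are untouched.

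**What to change.** Replace the exclusion sentence in SAP 9.1 with:

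> The number and percentage of values below LOQ will be tabulated per dose, visit and time cell. The median, and the minimum, will rank values below LOQ as lowest and be shown as BLQ where applicable. The geometric mean, its CI and the geometric CV will be estimated by maximum likelihood for left-censored lognormal data, and will not be reported or plotted where more than one third of values in the cell are below LOQ.

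One estimator should be named. LOQ/2 may appear as a sensitivity summary only, because it is itself about 11% low at a CV of 50% with 30% BLQ.

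The cost is SAP wording and minor programming, with no new data. The small downside is that some low-dose trough cells may show only a median and a BLQ count. If BLQ values turn out to be rare, the reported figures hardly change.

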13.4.2 Pharmacokinetic analyses

Blood concentrations of PSL and metabolites will be determined from blood samples obtained in the study, during the Titration and Maintenance Periods in order to investigate the PK of PSL and metabolites.

The PK parameters calculated include, $AUC_{(0-\tau)}$, AUC , C_{max} , t_{max} , $t_{1/2}$, C_{trough} , and $C_{max ss}$.

The PK variables will be derived from population PK modeling.

The PK parameters of PSL and metabolites will be listed and summarized using the following descriptive statistics: number of observations, geometric mean, lower and upper 95% CI, geometric coefficient of variation, arithmetic mean, SD, median, and minimum and maximum values. Graphical outputs over time will be produced on the trough plasma PSL concentrations.

Plasma concentration data for concomitantly administered AEDs will be assessed by evaluating ratios of steady state levels while on maintenance PSL vs Baseline (pre-PSL) levels.

An exploratory comparison of PSL blood levels derived from the MITRA samples with conventional venous sampling may be made. An exploratory evaluation of PSL metabolites may be undertaken.

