## 9.2 Plasma concentrations of concomitant AEDs

Blood samples for measurement of concomitant AED concentrations are collected at Visits 1, 2, 6, and 7. The concomitant AED concentrations will be summarized by visit and treatment group using the same descriptive statistics above (<LOQ values will be excluded) for the AED-PK-PPS. Only AED PK samples taken up to the (date of the last dose of study medication +1) will be included in the summary.

The AEDs investigated with mixed models will be those with data available for at least 10 evaluable subjects in one of the treatment groups (subset of AED-PK-PPS). An evaluable subject is defined as a subject:

- with at least one AED measure (>LOQ) at baseline and at least one AED assessment (>LOQ) during the maintenance period
- who received constant dose of AED for at least 14 days prior to the AED samples

Plasma concentration data for concomitantly administered AEDs (values <LOQ will be excluded) will be assessed by evaluating ratios of steady state levels during the Maintenance Period vs baseline levels. The baseline concentration is defined as the arithmetic mean concentration (if multiple concentrations are available at Visits 1 and 2) or the single concentration (if only 1 concentration is available at Visit 1 or Visit 2). Difference between log-transformed AED concentration at Visits 6 and 7 and baseline will be assessed using Mixed Model Repeated Measures (MMRM). The model will include log-transformed baseline concentration, visit, treatment, and treatment-by-visit interaction as fixed effects. An unstructured covariance structure will be used. If the model does not converge, an appropriate covariance structure will be used instead. Geometric least-squares (LS) means ratios and associated 90% CIs for each visit, by treatment group and PSL total will be calculated by exponentiation of the log-transformed data. Changes in AED concentration during the Maintenance Period and baseline will be considered clinically relevant if the respective 90% CIs fall entirely outside the conventional 0.80-1.25 limits. Forest plots will be provided on these (LS) means ratios and associated 90% CIs.

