**Has been changed to:**

**9.1 Plasma concentrations of PSL and its major metabolites**

Plasma concentrations of PSL and its major metabolites will be determined from blood samples obtained during the Titration and Stabilization and Maintenance Periods (Visits 3, 4, 5, 6 and 7). Individual concentrations of PSL and its [REDACTED] (from venous conventional sampling and dried blood (MITRA) sampling) and concentrations for the [REDACTED] will be listed for subjects in PSL treatment groups for the PK-Set and will include visit, actual daily dose (mg), date and time of the most recent administration, scheduled sampling time per the CRF, actual date and time of sampling, time interval between plasma sample and the most recent administration (in hours with 2 decimal places). Samples excluded from the PK-PPS will be marked in the listing.

. Values below the limit of quantification (LOQ) will be reported as BLQ (below the limit of quantification).

Concentrations of PSL and its [REDACTED] will be summarized by sampling method (venous, dried blood MITRA), PSL dose group, visit, and sampling times for the PK-PPS using the following descriptive statistics: number of observations, geometric mean, 95% CI of the geometric mean, geometric coefficient of variation, arithmetic mean, SD, median, and minimum and maximum values. Measured values below the LOQ will be set LOQ/2 for the calculation. Concentrations for [REDACTED] (only in venous blood) will also be summarized similarly.

Descriptive statistics of concentrations will be calculated if at least 2/3rd of the individual data points are quantifiable ( $\geq$ LOQ).

Of note, geometric mean is calculated as:  $\exp$  (arithmetic mean of log-transformed concentrations); upper and lower bounds of the 95% confidence interval (CI) of the geometric mean are calculated as  $\exp$  (upper) and  $\exp$ (lower) of the 95% CI of the arithmetic mean of log-transformed concentrations; geometric coefficient of variation is calculated as:  $100 \times \sqrt{[\exp(\text{variance of log-transformed concentrations}) - 1]}$ .

The PK samples will be summarized based on the actual time since the most recent dose using the following time categories:

- >0 to <45 min after dosage: 0.5h (30min)
- 45 to <75 min after dosage: 1h (60min)
- 75 to <105 min after dosage: 1.5h (90min)
- 105 to <150 min after dosage: 2h (120min)
- 150 to <210 min after dosage: 3h (180min)
- 4h: 3.5h to <4.5h
- 5h: 4.5 to <5.5h
- 6h: 5.5 to <6.5h
- 8h: 6.5 to <9h

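### SAP 9.1 as supplied omits the exponential from the geometric CV formula, so the result is undefined for log-variance below 1 and too small at or above 1.

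*SAP*

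**What the plan says.** SAP Section 9.1 lists the descriptive statistics for PSL and metabolite concentrations and then defines three of them in one sentence:

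- The geometric mean is the exponential of the "arithmetic mean of log-transformed concentrations".
- Its 95% confidence bounds are the exponentials of the bounds of the log-scale mean.
- The "geometric coefficient of variation is calculated as" 100 times a square root, and the expression under the root reads "variance of log-transformed concentrations}] - 1" (the stray brace is typesetting markup). The whole difference lies under the root, and the variance is not exponentiated.

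SAP Section 3.1 states that log-transformation uses the natural logarithm.

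The statistic is reused. SAP Section 9.2 summarises concomitant-AED concentrations "using the same descriptive statistics above". Protocol Section 13.4.2 also asks for "geometric coefficient of variation, arithmetic mean, SD, median" and other statistics for the PK parameters, but gives no formula. SAP 9.1 is therefore the only current definition in the two documents.

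**The concern.** A geometric CV expresses log-scale spread as a percentage on the original scale, which requires exponentiating the log-variance before subtracting 1. Without that step the formula subtracts 1 from the variance itself. For variances below 1 this asks for the square root of a negative number. For larger variances it returns a number that looks plausible and is wrong.

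A programmer who follows the SAP literally would get missing or understated entries. A programmer who uses the standard formula would get correct entries that do not match the written plan, and an independent validator working from the SAP would not reproduce them.

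**Working it through.** **Inputs**

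- Formula as printed: 100 × √(v − 1), from SAP 9.1.
- Log-normal form: 100 × √(exp(v) − 1). A log-normal variable with log-mean m and log-variance v has mean exp(m + v/2) and variance (exp(v) − 1) × exp(2m + v). Dividing the SD by the mean leaves √(exp(v) − 1).
- v is the "variance of log-transformed concentrations". The documents give no value, so every v below is an assumption, chosen to show the range.

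The plan states no numerical CV, so there is no figure to reproduce. The check compares the two formulas.

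**Step 1: where the printed formula exists.** v − 1 is negative for all v < 1. At v = 1 the correct value is 100 × √(2.718 − 1) = 131.1%. The printed formula is therefore undefined for every true geometric CV below about 131%.

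**Step 2: where it exists, is it right?** exp(v) is larger than v for every v, so √(v − 1) is always below √(exp(v) − 1). The printed result is too small throughout v ≥ 1.

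**Step 3: values**

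| Assumed v | With exponential | As printed |
|---|---|---|
| 0.04 | 20.2% | undefined |
| 0.25 | √(1.284 − 1) = 53.3% | undefined |
| 0.5 | 80.5% | undefined |
| 1.0 | 131.1% | √0 = 0.0% |
| 1.5 | √(4.482 − 1) = 186.6% | √0.5 = 70.7% |
| 2.0 | √(7.389 − 1) = 252.8% | √1 = 100.0% |

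A simulation of 1,000,000 log-normal draws gave a CV of 53.2% at v = 0.25 and 80.6% at v = 0.5, in agreement with the exponential form.

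**Step 4: other bracketings.** Reading the formula as 100 × (√v − 1) gives −50.0 at v = 0.25. Reading it as 100 × √v − 1 gives 49.0 there, against 53.3. Neither rescues it.

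**Step 5: likely intended form.** The amendment logs in SAP 14.1 (Change #14) and SAP 14.2 (Change #9, before and after text) print "\exp(\text{variance of log-transformed concentrations}) - 1" under the root. These are superseded texts and serve only to indicate what was meant. The current formula is wrong on its own terms.

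**The case against.** The strongest objection is that the sponsor's SAP may be correct. The text was read from PDF by a program, and the finding rests on one missing token. The bracket placement leaves room for doubt. In the amendment logs the square bracket encloses the whole difference; in Section 9.1 it encloses only the variance, where the exponential's parentheses would have been. A misreading could produce that, and so could an editing slip.

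This objection stands as a reason to check the source file, but it does not dispose of the point. The exponential was read correctly three times in the same sentence (the geometric mean and both bounds) and in all three log printings of the formula. Section 9.1 was also edited after the Amendment 2 text without an entry in the Amendment 3 list, which covers only major changes. For example, values below the limit of quantification went from half the limit to excluded. An unlogged slip is therefore plausible, though not proven.

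A reader might also infer that the SAP contradicts itself because the logs differ from Section 9.1. That does not follow, since a log describes superseded text.

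Finally, for v < 1 the error announces itself, because software returns a missing value or an error. Only v ≥ 1 gives a silently wrong number, and nothing in the documents shows that any PK stratum reaches that.

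**Conclusion.** The formula in SAP 9.1 as supplied is wrong: undefined for v < 1 and too small for v ≥ 1. The algebra rests on no assumption about the data. The illustrative percentages rest on assumed log-variances. Whether the slip is the sponsor's or arose in text extraction cannot be settled from the supplied text.

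The effect is confined to the geometric CV entry in the descriptive concentration tables for PSL and metabolites, and in the AED tables that reuse those statistics. A reader might infer that the PK tables lose their measure of dispersion, or that the drug-interaction conclusions are at risk. The documents support neither reading. The SD, the minimum and maximum, and the geometric mean with its confidence interval are unaffected. The AED assessment in SAP 9.2 uses mixed-model ratios with 90% confidence intervals, which do not use the geometric CV. No efficacy analysis, significance level or sample size depends on it. This is a minor correction.

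**What to change.** Check Section 9.1 in the source file. If the exponential is present there, the point closes with no change. If it is absent, correct the definition to 100 × √[exp(v) − 1], with v the variance of the log-transformed concentrations, and confirm that the programs for the Section 9.1 and 9.2 tables use that form. The cost is one formula in the SAP and a short program check, with no consequence for design or data collection.
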